In this section, we focus on the null scenarios and type I error rates. The type I error rate of the design is a function of the model analysis, number of arms, the sample size, and the design. In addition, the accrual rate (which dictates the amount of follow-up), the drop-out rate, the distribution of the entry EYO, and the behavior of the natural history of the cognitive endpoint all can affect the type I error rate of the trial. In order to control the type I error rate, we simulate across a wide range of assumptions for these parameters and demonstrate that the analysis controls the type I error rate at a one-sided 2.5% rate for each treatment arm. The threshold for success 0.9837 at the final analysis is selected through simulation in order to control the type I error rate. The primary DIAN-MCE analysis is based on the posterior probability of superiority ($CPR < 1$). That is, if in the final analysis the posterior probability of success is greater than the cut-off X , we will label the trial a success. We select the value of X in order to control type I error rate. In this section, we describe the procedure used to select X . In addition, we provide a post-trial bootstrap simulation procedure to verify the appropriateness of the type I error rate. The procedure used to create the threshold, X , is simulated from a set of 11 null hypotheses. Each scenario above is simulated under the null hypothesis (no treatment effect) for pooling of placebo from the other drug arm and for no pooling. This explores a range of assumptions for the execution parameters (accrual rate, drop-out rate), subject behavior (EYO distribution, rate of decline for placebo), treatment effect (non-constant and constant hazards), and test variability (error standard deviation). For each of the null scenarios, 5,000 simulated trials are presented, with 50,000 draws from each MCMC algorithm to calculate posterior probabilities.

- Simulate the full trial out to the time of the final analysis. Record the posterior probability of superiority at each of the final analyses.
- Select a value of X , such that the proportion of trials under the 11 null assumptions that meets the conditions is 2.5% or less.

Under each of the null scenarios, we simulate the final analysis and record the 97.5th percentile of the posterior probability of superiority for all the simulated trials. This 97.5th percentile is presented in [Table 11](#).

Table 11: The 97.5th Percentile of the Posterior Probability of Superiority for the Null Hypothesis Scenarios. Using this value as the threshold in that scenario would create a type I error rate of 2.5%.

Simulation Scenario	Threshold, X	
	No Pooled Placebos	Pooled Placebos
Base	0.9417	0.9376
Smaller EYO	0.9837	0.9811
Larger EYO	0.8820	0.9259
Slower Accrual	0.9429	0.9487
Faster Accrual	0.9432	0.9488
2.5% Annual Drop-Out	0.9469	0.9380
10% Annual Drop-Out	0.9374	0.9534
Steeper Curve	0.9333	0.9448
Shallower Curve	0.9717	0.9683
Increased SD	0.9481	0.9426
Decreased SD	0.9437	0.9631

The maximum value needed to control the type I error rate across all the null scenarios is 0.9837. This value is used as the threshold for superiority in the final analysis.

The results for all simulations shown above are based on this cut-off, 0.9837, for superiority. In this section, we present the probability of success for each of the null hypothesis scenarios in [Table 12](#).

Table 12: Type I Error Rate for Each Scenario with/without Concurrently Randomized Placebos

Simulation Scenario	Type I Error Rate Probability	
	No Pooled Placebos	Pooled Placebos
Base	0.009	0.005
Smaller EYO	0.025	0.022
Larger EYO	0.003	0.005
Slower Accrual	0.005	0.010
Faster Accrual	0.007	0.005
2.5% Annual Drop-Out	0.008	0.007
10% Annual Drop-Out	0.008	0.008
Steeper Curve	0.004	0.009
Shallower Curve	0.015	0.014
Increased SD	0.005	0.005
Decreased SD	0.009	0.012

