3.3 Study Population for Solanezumab and Gantenerumab

The study population consists of individuals who either are known to have an Alzheimer's disease (AD) causing mutation or who don't know their gene status but are "at risk" for an autosomal dominantly inherited Alzheimer's disease (DIAD) mutation. To be eligible for the trial, subjects (mutation positive and negative subjects) must be either 1) cognitively normal between 15 years younger (-15) to 10 years older (+10) than their expected age at cognitive symptom onset or 2)

have mild symptoms of dementia (CDR 0.5 or 1) and are within +10 years of onset of the symptoms of dementia. Other inclusion criteria are specified in the protocol.

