In order to characterize and understand the performance of the design and to identify values to support the model for the cognitive composite analysis, we carried out detailed simulations of the design under multiple scenarios as described in this section. The trial is simulated as described, including the accrual and randomization of subjects, pooling of placebos, dropout rates of subjects and the timing of the analyses as detailed here. A variety of scenarios are simulated with the operating characteristics summarized. The base case scenario presents the best estimates for each of the parameters used to simulate the trial and subjects. The remaining 10 scenarios explore the sensitivity of the design to different possible truths. The assumptions made in this section are based on an analysis of the DIAN-OBS cohort (Data Freeze 9). This section provides an estimate of the power and type I error rate for both study drugs.

In particular, we make the following assumptions for our base simulations:

- **Regimen Size:** 69 mutation positive subjects with 3:1 randomization (active to placebo)
- **Number of Regimen Cohorts:** Simultaneous enrollment of another arm while one study drug is enrolling patients, hence receiving a randomization of 50% of the accrued subjects and the ability to borrow approximately 17 placebo subjects.
- **Distribution of EYO at enrollment:** Uniform between –15 and +10 EYO
- **Expected Natural Cognitive Progression:** All new placebo subjects behave like the cognitive endpoint model (with assumed monotonically decreasing cognitive mean values) estimates from the DIAN-OBS data, with respective variability of new measurements. In particular, the assumed model for simulating subjects is

$$Y_{ij} = \gamma_i + f(EYO_{ij} - \delta_i | \hat{\alpha}) + \epsilon_{ij}$$

$$\begin{aligned} \gamma_i &\sim N(0, 1^2) \\ \delta_i &\sim N(0, 2^2) \\ \epsilon_{ij} &\sim N(0, 0.333^2) \end{aligned}$$

$$f(x) = \begin{cases} 0 & x \leq -15 \\ (1 + [x] - x)\alpha_{[x]} + (x - [x])\alpha_{[x]+1} & -15 < x \leq 15 \\ \alpha_{15} & x > 15 \end{cases} \quad (1)$$

The estimates of the rate of decline for the natural history (control) subjects from the observational data are presented in Table 8.

Table 8: Posterior Mean and Standard Deviation of the Aging Curve for the Model Assuming a Monotonically Decreasing Rate from the DIAN-OBS Data Freeze 9.

α_{EYO}	Posterior Mean	Posterior Standard Deviation
α_{-15}	0	0
α_{-14}	-0.07	0.06
α_{-13}	-0.14	0.08

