α_{-12}	-0.21	0.09
α_{-11}	-0.27	0.09
α_{-10}	-0.33	0.10
α_{-9}	-0.39	0.10
α_{-8}	-0.46	0.11
α_{-7}	-0.53	0.11
α_{-6}	-0.61	0.12
α_{-5}	-0.68	0.12
α_{-4}	-0.76	0.12
α_{-3}	-0.83	0.13
α_{-2}	-0.90	0.13
α_{-1}	-0.98	0.14
α_0	-1.06	0.14
α_1	-1.20	0.18
α_2	-1.40	0.29
α_3	-1.70	0.41
α_4	-2.15	0.44
α_5	-2.66	0.38
α_6	-2.93	0.34
α_7	-3.11	0.38
α_8	-3.37	0.37
α_9	-3.71	0.24
α_{10}	-3.86	0.24
α_{11}	-4.07	0.27
α_{12}	-4.29	0.37
α_{13}	-6.10	0.94
α_{14}	-7.77	1.51
α_{15}	-9.22	1.73

- **Frequency of Cognitive Assessments:** Every 12 months
- **Dropout:** 5% annual drop-out rate unrelated to outcome
- **Accrual:** 5 mutation positive subjects per month total across all enrolling regimen cohorts
- **CDR-Global:** The trial has an inclusion criterion of a CDR-global of 1 or less. For each subject a CDR-global is simulated based on their baseline cognitive composite. A subject is excluded (and replaced) if a CDR-global greater than 1 is simulated.

The CDR-global is simulated, correlated to the DIAN-TU Cognitive Composite, based on a model from Data Freeze 9. The details of CDR-global simulation are presented in the following section with full details on subject-level simulations.

The assumptions for simulating a virtual subject follow.

Subject Simulation

In this section, we describe the simulation of an individual subject. This is described for the base scenario. The simulation of a virtual subject is conducted as the following:

1. A time of accrual is simulated based on a Poisson process with a mean weekly accrual rate of 5 per month (4 weeks). If two regimens are accruing, then the accrual will be half of the assumed rate.
2. A value of baseline EYO is simulated (EYO_0). In the base case this is simulated as a uniform value over the integers from -15 to 10 (inclusive). This subject is not necessarily enrolled – a simulation of the composite cognitive values and CDR-global is conducted to determine if the additional entry criterion of $CDR\text{-}global \leq 1$ is met.
 - a. An additive random effect for the subject is simulated: $\gamma_i \sim N(0,1)$
 - b. A random effect for EYO for the subject is simulated: $\delta_i \sim N(0,2)$
 - c. A baseline cognitive score, Y_{i0} , is simulated from the distribution:

$$Y_{i0} \sim N(\gamma_i + f(EYO_0 - \delta_i), 0.333^2)$$

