- d. A CDR-global is simulated conditional on the baseline cognitive score. Using the observational study, the distribution of the cognitive composite for each CDR-global value was calculated and approximated by a normal distribution. Thus, the

mean and standard deviation for the composite cognitive conditional on CDR-global of 0, 0.5, 1, and 2 or larger was calculated (Table 9).

- e. The simulation of CDR-global conditional on composite cognitive value is calculated using Bayes theorem with prior probabilities of 0.603, 0.225, 0.072, and 0.10, respectively, and normal distributions of the cognitive composite given CDR-global with means and standard deviations from Table 9. If the simulated CDR-global is 1 or less, then the subject is admitted to the trial and post-baseline observations are simulated. If the subject has a CDR-global value larger than 1, then the subject is rejected and a new subject is simulated (go back to Step 2).

Table 9: Distribution of the Cognitive Composite Z-Score Given CDR-global Status in the Observational Data

CDR-Global	Number	Mean Composite Cognitive	Standard Deviation of Composite Cognitive
0	221	-0.11	0.61
0.5	135	-1.26	0.80
1	58	-2.51	0.58
2+	26	-3.35	0.37

3. The post-baseline observations are simulated assuming a treatment CPR value (1 for placebo, and depending on the scenario different values of CPR for the treatment regimen):

$$Y_{ij} \sim N(\gamma_i + f(EYO_0 - \delta_i) + CPR[f(EYO_j - \delta_i) - f(EYO_0 - \delta_i)], 0.333^2) \text{ for } j = 1, \dots, n_i.$$

A drop-out time is simulated for every subject. This is simulated assuming an exponential time to drop-out matching the assumption of the annual drop-out rate within 52 weeks. At each time of analysis, if the subject has dropped out, then their cognitive values from that point forward are ignored in the analysis.

Scenarios

The remaining scenarios explore the following scenario variations:

- A. Base scenario
- B. No pooling placebos: The base scenario with no pooled placebo from the other active drug arm.
- C. Simulate different distributions of the EYO at entry. One scenario is biased toward smaller EYO (a Beta(1,2) scaled between -10 and 15) values and the other is biased toward larger EYO values (a Beta(2,1) distribution scaled between -10 and 15).
- D. Simulate different accrual rates. A scenario with an accrual rate that is 8 subjects per month (faster) and a scenario with 3 subjects per month (slower).

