- E. Simulate varying drop-out rates. A scenario with an annual drop-out rate of 2.5% per year and a scenario with an annual drop-out rate of 10% per year.
- F. Simulate different standard deviations. One scenario has a standard deviation that is 25% higher ($0.333 \times 1.25 = 0.416$) and one has a standard deviation that is 25% smaller ($0.333 \times 0.75 = 0.250$).
- G. Simulate different cognitive means as a function of EYO (the assumed α parameters in the model). One scenario simulates a steeper mean curve. The default values of α used to simulate virtual subjects are increased by 25%. A second scenario simulates a shallower mean curve. The default values of α used to simulate virtual subjects are decreased by 25%.

In each scenario with a positive treatment benefit we simulate 1000 trials and 50,000 draws from each Markov chain Monte Carlo (MCMC) algorithm to calculate posterior probabilities. Each trial simulates the final analysis at 4 years (based on timing of the last subject in the cohort). The simulation for null scenarios (no treatment effect) and the ramifications for the type I error rate are discussed in the next section. For the null scenarios, 5,000 simulated trials are presented, with 50,000 draws from each MCMC algorithm to calculate posterior probabilities. The power for all the scenarios is presented in [Table 10](#).

Table 10: Power for Each Study Drug Arm for Various Treatment Effect Sizes and Assumptions

Treatment Effect*	Base	No Pooled Placebo	Smaller EYO	Larger EYO	Drop Outs 2.5%	Drop Outs 10%	Faster Accrual	Slower Accrual	Steeper Curve	Shallower Curve	Increased SD	Decreased SD
0%	0.005	0.009	0.022	0.005	0.007	0.008	0.005	0.010	0.009	0.014	0.005	0.012
10%	0.071	0.035	0.089	0.096	0.075	0.048	0.041	0.125	0.119	0.083	0.049	0.142
20%	0.345	0.141	0.272	0.499	0.349	0.255	0.214	0.557	0.427	0.309	0.237	0.538
30%	0.721	0.406	0.582	0.866	0.750	0.621	0.568	0.887	0.797	0.640	0.554	0.881
40%	0.938	0.736	0.833	0.986	0.962	0.885	0.875	0.983	0.962	0.900	0.843	0.981
50%	0.991	0.930	0.958	0.999	0.996	0.986	0.987	0.998	0.997	0.983	0.978	0.997
60%	1.000	0.991	0.996	1.000	1.000	0.998	0.998	1.000	1.000	1.000	0.997	1.000
70%	1.000	1.000	0.999	1.000	1.000	0.999	1.000	1.000	1.000	1.000	1.000	1.000

*Reduction in cognitive progression as measured by the CPR.

Type I Error Rate

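### Appendices V and VI define the Smaller EYO and Larger EYO scenarios on -10 to 15 instead of -15 to +10; as printed, Smaller EYO, which sets the 0.9837 composite threshold, is not smaller than base

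*SAP*

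**What the plan says.** Appendix V, in its base assumptions, takes entry EYO as "Uniform between –15 and +10 EYO", and its subject-simulation steps draw it over the same span. Appendix VI uses the same span for its base case. The EYO strata in Table 1 run from -15 to +10, the DIAN-OBS selection rule in Section 7.2 uses the same limits, and Section 3.3 admits subjects who are "cognitively normal between 15 years younger (-15) to 10 years older (+10) than their expected age at cognitive symptom onset".

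Appendix V, Scenarios, item C departs from this range: "One scenario is biased toward smaller EYO (a Beta(1,2) scaled between -10 and 15) values". The companion scenario is "biased toward larger EYO values (a Beta(2,1) distribution scaled between -10 and 15". Appendix VI, Simulation Scenarios, item B repeats both definitions. Neither appendix explains the change of range.

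The results are then used to set a threshold. The Table 11 row reads "Smaller EYO 0.9837 0.9811" (without and with pooled placebos), and the text below it concludes: "The maximum value needed to control the type I error rate across all the null scenarios is 0.9837". The Table 10 row for a 30% effect begins "30% 0.721 0.406 0.582 0.866", in the order base, no pooled placebo, Smaller EYO, Larger EYO.

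**The concern.** Shifting the range by five years undoes the purpose of the Smaller EYO scenario. Beta(1,2) leans toward the low end of its range, but the low end has moved from -15 to -10, so the printed distribution sits later than base on average. The scenario should represent a trial that enrolls early, slowly declining subjects. Appendix V itself names the entry-EYO distribution as something that can change the type I error rate, and this scenario carries the evidence for an early-stage population.

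It is also the one scenario that fixes 0.9837. If the printed range was simulated, type I error control was not examined for a population earlier than base, and the threshold came from a scenario that does not match its label. If another range was simulated, the SAP misstates the definition of the scenario that sets the threshold, and a reader who codes it as printed would simulate a different population.

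**Working it through.** **1. Plan's own figure.** The largest of the 22 entries in Table 11 is 0.9837 (Smaller EYO, no pooled placebos), which matches the stated threshold. The largest entry outside the two EYO scenarios is 0.9717 (Shallower Curve, no pooling). The percentiles themselves need the Bayesian code and were not reproduced.

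**2. Raw distributions (exact).** A Beta(a,b) scaled to a 25-year range with lower limit L has mean L + 25a/(a+b).

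- Base: (-15 + 10)/2 = -2.5.
- Smaller, as printed: -10 + 25/3 = -1.67. On -15 to +10: -15 + 25/3 = -6.67.
- Larger, as printed: -10 + 50/3 = 6.67. On -15 to +10: -15 + 50/3 = 1.67.
- Share above +10 as printed, where the cut is at 20/25 = 0.8: Smaller (1 - 0.8)² = 0.04; Larger 1 - 0.8² = 0.36.
- Share below -10: Smaller as printed 0; on -15 to +10, 1 - (1 - 5/25)² = 0.36.

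**3. Decline among admitted subjects.** This is a Monte Carlo of the Appendix V subject generator: Table 8 curve, subject effect SD 1, EYO effect SD 2, residual SD 0.333, and the CDR-global filter with Table 9 and prior probabilities 0.603, 0.225, 0.072, 0.10. Decline is f(EYO - δ) minus f(EYO + 4 - δ), averaged over admitted subjects.

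| Scenario | Mean admitted EYO | 4-year decline |
|---|---|---|
| Base (integer draws; continuous draws give 0.71) | -3.9 | 0.728 |
| Smaller, as printed | -2.6 | 0.723 |
| Smaller, -15 to +10 | -7.1 | 0.461 |
| Larger, as printed | 5.9 | 1.499 |
| Larger, -15 to +10 | 0.3 | 1.025 |

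**4. Which range fits Table 10?** Three scenarios differ only in the steepness of the curve, with these declines and stated powers at a 30% effect: Shallower (0.578, 0.640), Base (0.728, 0.721), Steeper (0.947, 0.797). The least-squares line is approximately power = 0.404 + 0.420 × decline.

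| Scenario | Predicted, as printed | Predicted, -15 to +10 | Stated |
|---|---|---|---|
| Smaller EYO | 0.708 | 0.598 | 0.582 |
| Larger EYO | 1.03 (beyond the line's valid range) | 0.835 | 0.866 |

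The same approach applied to the no-pooling percentile in Table 11 predicts 0.952 for Smaller as printed and 0.978 on -15 to +10, against 0.9837 stated.

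**5. Appendix VI, CPR 0.70.** Base power is 0.959. With the 0.981 threshold, power is approximately Φ(z·√r - 2.075), where z = 1.739 + 2.075 = 3.814 and r is information relative to base. The stated 0.764 implies √r = (0.719 + 2.075)/3.814 = 0.733, so r = 0.54. The stated 0.993 implies √r = (2.457 + 2.075)/3.814 = 1.188, so r = 1.41. From the Table 13 curves, Smaller as printed keeps about 98-99% of base information (power about 0.955-0.958), and on -15 to +10 about 72% (about 0.875). The stated drop therefore points toward -15 to +10, but neither range reproduces 0.764. The 0.993 is too near the ceiling to carry much weight alone.

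**6. Primary threshold.** In Table 16 Larger and Smaller EYO give 0.9713 and 0.9723. The maximum is Slower Decline at 0.9801, so the EYO scenarios do not determine 0.981 as tabulated.

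**The case against.** The strongest reply is that this is a misprint with no numerical consequence. The SAP does not say which range was coded, and its Appendix V power values fit -15 to +10. If that range was run, 0.9837 stands and only two lines of text are wrong. This largely holds, and it is the likelier explanation. It is not proven: the fit is a straight line through three scenarios, a simplified version of the model gave base power 0.758 against the stated 0.721, and the Appendix VI figure is missed by about 11 points (0.875 against 0.764) even on -15 to +10.

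The reach of 0.9837 is also limited. It belongs to the univariate model for the cognitive composite (Section 12.1.9), run in the mITT population only, and not to the primary multivariate analysis.

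Three stronger readings are tempting and should not be made.

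- A reader might infer that subjects above EYO +10 could never enroll. The EYO limit in Section 3.3 attaches to cognitively normal subjects; the symptomatic route is worded in years from onset of dementia symptoms. What can be said is that such draws lie beyond the last Table 1 stratum and outside the base simulation.
- A reader might infer that the parties validating the software cannot reproduce the scenario. Section 12.3.2.2 describes testing the analysis package on simulated data; it does not say that they rerun these scenarios.
- A reader might infer that the published tables cannot have come from the printed range. The evidence favors the other range but does not exclude this one.

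**Conclusion.** The inconsistency is certain, and it appears in both appendices. The scaled means and tail shares are exact: as printed, Smaller EYO is centered 0.83 years later than base (-1.67 against -2.5) and declines about as fast, so its definition contradicts its label. The definition affected is the one that alone sets 0.9837.

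The numerical consequence is conditional. If -15 to +10 was run, nothing changes but the text. If -10 to 15 was run, early-entry type I error was not tested as labeled, and 0.9837 needs re-deriving; its corrected value cannot be computed without the model code. It would be wrong to conclude that the primary threshold is compromised: as tabulated, 0.981 is governed by Slower Decline (0.9801). It would come into question only if the printed range was run and a corrected rerun gave a percentile above 0.981.

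The conclusion on which range was run rests on the SAP's own curves and CDR filter and on an approximately linear relation of power to decline.

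**What to change.** 1. Check the simulation code for the range used in Appendix V item C and Appendix VI item B. Do this before editing, so that the text does not misreport what was run.
2. If -15 to +10 was run, correct the range in both appendices and keep all figures.
3. If -10 to 15 was run, rerun the two EYO scenarios on -15 to +10 under null and alternative in each appendix. Update the EYO entries of Tables 10-12 and 15-16, re-derive 0.9837, and revise 0.981 only if a rerun percentile exceeds it. If 0.9837 changes, the other entries of Tables 10 and 12 must be recalculated at the new cut-off from the stored posterior probabilities.

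The cost is a code check and two lines of text. At worst, two scenarios are rerun in each appendix, with no change to trial conduct or data collection.

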20 APPENDIX VI. DETAILS OF CLINICAL TRIAL SIMULATIONS FOR DIAN-MCE

In order to characterize and understand the performance of the primary DIAN-MCE analysis, we carried out detailed simulations of the design under multiple scenarios as described in this section. The trial is simulated as described, including the accrual and randomization of subjects, pooling of placebos, inclusion of simulated DIAN-OBS data, drop-out rates of subjects and the timing of the analysis as detailed here. A variety of scenarios are simulated with the operating characteristics summarized. The base case scenario presents the best estimates for each of the parameters used to simulate the trial and subjects. The remaining 7 scenarios explore the sensitivity of the design to different possible truths. The assumptions made in this section are based on an analysis of the DIAN-OBS cohort (Data Freeze 11). This section provides an estimate of the power and type I error rate for each study drug.

In particular, we make the following assumptions for our base simulations:

- **Regimen Size:** 70 mutation positive subjects with 3:1 randomization (active to placebo) per arm (53:17 per arm, for 53:53:34 for each arm and the pooled placebo)
- **Distribution of EYO at enrollment:** Uniform between -15 and +10 EYO with a simulation of CDR-global as a function of EYO for trial inclusion ($CDR \leq 1$)

Modeling Cognitive Endpoint Progression: The assumed model for simulating subjects is assumed for simulating virtual subject data. Let \tilde{Y}_{ij} be the 4-dimensional vector of outcomes for subject i , at their j th visit. Let E_{ij} be the estimated years to symptom onset for subject i at visit j .

The distribution for each observation is assumed to be normally distributed:

$$\tilde{Y}_{ij} \sim N_4(\tilde{\mu}_{ij}, \Sigma).$$

The mean for variable v is modeled as

$$\mu_{ijv} = \gamma_{iv} + f(E_{i0} - \delta_i | \alpha_v) + \exp(\theta_{T_i}) [f(E_{ij} - \delta_i | \alpha_v) - f(E_{i0} - \delta_i | \alpha_v)]$$

where the random effect for variable v is simulated as

$$\gamma_{iv} \sim N(0, 1^2) \quad v=1, 2, 3, 4.$$

The random effect for EYO adjustment is simulated as

$$\delta_i \sim N(0, 2^2).$$

The variance-covariance matrix, Σ , is assumed to (estimated from the DIAN-OBS data) have standard deviations of 0.329, 3.431, 0.280, 0.290 for MEMUNITS, MMSE, WAIS, ISLT, respectively. The pairwise correlations are 0.091 (MEMUNITS and MMSE), 0.136 (MEMUNITS and WAIS), 0.089 (MEMUNITS and ISLT), 0.419 (MMSE and WAIS), -0.088 (MMSE and ISLT), and -0.070 (WAIS and ISLT).

The mean function for each component is

$$f(x) = \begin{cases} 0 & x \leq -15 \\ (1 + [x] - x)\alpha_{[x]} + (x - [x])\alpha_{[x]+1} & -15 < x \leq 15. \\ \alpha_{15} & x > 15 \end{cases}$$

The assumed mean changes as a function of the EYO values for the observational data are presented in Table 13.

Table 13: The Mean for Each Endpoint

α_{EYO}	MEMUNITS	MMSE	WAIS	ISLT
α_{-15}	0	0	0	0
α_{-14}	-0.111	-0.118	-0.093	-0.116
α_{-13}	-0.224	-0.238	-0.192	-0.235
α_{-12}	-0.341	-0.360	-0.297	-0.351
α_{-11}	-0.462	-0.481	-0.404	-0.457
α_{-10}	-0.585	-0.605	-0.513	-0.555
α_{-9}	-0.706	-0.730	-0.622	-0.647
α_{-8}	-0.824	-0.860	-0.736	-0.738
α_{-7}	-0.941	-0.993	-0.853	-0.831
α_{-6}	-1.054	-1.134	-0.974	-0.928
α_{-5}	-1.166	-1.284	-1.100	-1.030

α_{EYO}	MEMUNITS	MMSE	WAIS	ISLT
α_{-4}	-1.276	-1.445	-1.234	-1.134
α_{-3}	-1.388	-1.618	-1.382	-1.242
α_{-2}	-1.511	-1.806	-1.553	-1.351
α_{-1}	-1.653	-2.014	-1.754	-1.458
α_0	-1.817	-2.260	-1.987	-1.558
α_1	-1.990	-2.258	-2.238	-1.646
α_2	-2.161	-3.024	-2.520	-1.724
α_3	-2.336	-3.686	-2.841	-1.792
α_4	-2.536	-4.652	-3.158	-1.856
α_5	-2.750	-6.008	-3.506	-1.919
α_6	-2.950	-7.824	-3.648	-1.990
α_7	-3.123	-9.959	-4.035	-2.077
α_8	-3.272	-12.193	-4.645	-2.189
α_9	-3.436	-14.155	-5.065	-2.325
α_{10}	-3.650	-15.482	-5.314	-2.505
α_{11}	-3.850	-16.500	-5.501	-2.650
α_{12}	-4.050	-17.500	-5.700	-2.800
α_{13}	-4.250	-18.500	-5.900	-2.295
α_{14}	-4.450	-19.500	-6.100	-3.100
α_{15}	-4.650	-20.500	-6.300	-3.250

- **Frequency of cognitive assessments:** Every 12 months
- **Dropout:** 7% annual drop-out rate unrelated to outcome
- **Accrual:** The actual trial accrual is used. The 140 subjects are accrued over 975 days with the 35th, 70th, and 105th being enrolled on days 589, 758, and 918, respectively.
- **CDR-Global:** The trial has an inclusion criterion of a CDR-global of 1 or less. For each subject, a CDR-global is simulated based on their baseline cognitive composite. The simulated cognitive composite is calculated, and a subject is excluded (and replaced) if a CDR-global greater than 1 is simulated.

The details of CDR-global simulation are presented in the following section with full details on subject-level simulations.

Subject Simulation

In this section, we describe the simulation of an individual subject. This is described for the base scenario. The simulation of a virtual subject is conducted as the following:

1. The accrual day is specified.
2. The treatment assignment is permuted over all subject (53, 53, and 34 as described above).
3. A value of baseline EYO is simulated (EYO_0). In the base case, this is simulated as a uniform random variable from -15 to 10 . This subject is not necessarily enrolled – a simulation of the baseline composite cognitive values and CDR-global is conducted to determine if the additional entry criterion of $CDR\text{-}global \leq 1$ is met.
 - a. An additive random effect for the subject is simulated: $\gamma_i \sim N(0, 1^2)$
 - b. A random effect for EYO for the subject is simulated: $\delta_i \sim N(0, 2^2)$
 - c. A baseline vector, Y_{i0} , is simulated from the distribution above.
 - d. A CDR-global is simulated conditional on the baseline cognitive score. Using DIAN-OBS study, the distribution of the cognitive composite for each CDR-global value was calculated and approximated by a normal distribution. Thus, the mean and standard deviation for the composite cognitive conditional on CDR-global of 0, 0.5, 1, and 2 or larger was calculated (Table 14).
 - e. The simulation of CDR-global conditional on composite cognitive value is calculated using Bayes theorem with prior probabilities of 0.603, 0.225, 0.072, and 0.10, respectively, and normal distributions of the cognitive composite given CDR-global with means and standard deviations from Table 14. If the simulated CDR-global is 1 or less, then the subject is admitted to the trial and post-baseline observations are simulated. If the subject has CDR-global value larger than 1, then the subject is rejected, and a new subject is simulated (go back to Step 2).

Table 14: Distribution of the Cognitive Composite Z-Score Given CDR-global Status in the Observational Data

CDR-Global	Number	Mean Composite Cognitive	Standard Deviation of Composite Cognitive
0	221	-0.11	0.61
0.5	135	-1.26	0.80
1	58	-2.51	0.58
2+	26	-3.35	0.37

4. The post-baseline observations are simulated assuming a treatment CPR value for the respective treatment arm (each scenario/case assumes a value for placebo and each treatment arm). A CPR of 1 corresponds to being identical to the natural history (DIAN-OBS data). The treatment effect is incorporated to the mean for each variable as

$$\mu_{ijv} = \gamma_i + f(EYO_{i0} - \delta_i) + CPR[f(EYO_{ij} - \delta_i) - f(EYO_{i0} - \delta_i)] \text{ for } j = 1, \dots, n_i.$$

A drop-out time is simulated for every subject. This is simulated assuming an exponential time to drop-out matching the assumption of the annual drop-out rate within 52 weeks. At each time of analysis, if the subject has dropped out, then their cognitive values from that point forward are ignored in the analysis.

For the base case, 66 DIAN-OBS subjects are assumed. The follow-up is simulated as uniformly distributed from 3 to 6 years (meaning 3, 4, or 5 years of exposure are equally likely). All other components are simulated as above.

Simulation Scenarios

The following scenarios are simulated. In each scenario, 6 cases are simulated. The cases assume the target treatment arm has a CPR of 1, 0.80, 0.75, 0.70, 0.65, and 0.60. The following scenarios are simulated:

-
- A. Base scenario (described above)
- B. Simulate different distributions of the EYO at entry. One scenario is biased toward smaller EYO (a Beta(1,2) scaled between -10 and 15) values and the other is biased toward larger EYO values (a Beta(2,1) distribution scaled between -10 and 15).
- C. Simulate varying drop-out rates. A scenario with an annual drop-out rate of 3% per year and a scenario with an annual drop-out rate of 10% per year.
- D. Simulate different variance-covariance assumptions. The following scenarios are simulated: (1) the correlation between each pairwise measure is 0.25; (2) the correlation between each pairwise measure is 0.50; (3) the endpoints are uncorrelated; (4) each standard deviation is increased by 25%; (5) each standard deviation is decreased by 25%.
- E. Rate of decline. Two variations on the assumed rates of decline are simulated. We assume a 10% slower rate of decline for all endpoints and then a scenario with 10% faster rate of decline for all endpoints. These rates are assumed across the entire range of EYO, multiply each alpha in [Table 13](#) by 0.90 or 1.10, for all arms and all OBS data.
- F. Dosing effects. Each patient underwent a dosing change in the trial. The effects for the active arms are assumed to potentially change upon dosing. The treatment effect parameter is assumed for the high dose. The relative effect of the low dose to the high dose is varied. The default assumptions above have the low dose effect equal to the high dose effect. Proportions of 0.75, 0.50, 0.25, and 0 are simulated. The timing of the dose change is assumed to be after 3 years for the first 14 subjects, after 2 years for the next 111 subjects, and after 1 year for the last 16 subjects.
- G. Differing DIAN-OBS sample size. Sample size of 120 is simulated. The inclusion of run-in data from the DIAN-OBS data may be more equivalent to 120 DIAN-OBS data being “borrowed.”
- H. Simulate variation between the DIAN-OBS data and the randomized arms. In each of these scenarios, all randomized arms are simulated as having proportional changes from the DIAN-OBS data. Proportional effects of 0.80, 0.90, 1.10, and 1.20 are assumed.

In each case, within each scenario we simulate 1000 trials. Each MCMC simulates 20,000 draws from the MCMC algorithm, with a burn-in of 5000 to calculate posterior probabilities. Each trial simulates the final analysis when the last patient reaches 4 years. The power values for all the scenarios are presented in [Table 15](#).

Table 15: Power for Each Study Drug Arm for Various Treatment Effect Sizes and Assumptions

Treatment Arm CPR*	A	B		C		D				
	Base	Larger EYO	Smaller EYO	Drop Outs 3%	Drop Outs 10%	0.25 Correlation	0.5 Correlation	0 Correlation	Increased SD 25%	Decreased SD 25%
1	0.013	0.015	0.016	0.016	0.015	0.016	0.012	0.010	0.017	0.010
0.80	0.662	0.843	0.406	0.746	0.632	0.654	0.653	0.794	0.539	0.880
0.75	0.861	0.965	0.589	0.907	0.837	0.845	0.831	0.927	0.717	0.978
0.70	0.959	0.993	0.764	0.981	0.930	0.946	0.936	0.982	0.857	0.996
0.65	0.983	0.998	0.896	0.993	0.982	0.983	0.979	0.993	0.960	1
0.60	0.996	0.998	0.949	0.997	0.997	0.998	0.995	0.998	0.986	1

*Treatment effect is the reduction in cognitive progression as measured by the (1-CPR) relative to the blinded placebo arm

Treatment Arm CPR*	E		F				G
	Slower Decline	Faster Decline	Low = 0.75	Low = 0.50	Low = 0.25	Low = 0	OBS N = 120
1	0.023	0.011	0.013				0.009
0.80	0.673	0.727	0.622	0.551	0.488	0.338	0.706
0.75	0.831	0.909	0.816	0.745	0.679	0.514	0.889
0.70	0.935	0.981	0.934	0.872	0.822	0.669	0.960
0.65	0.984	0.997	0.979	0.950	0.906	0.816	0.990
0.60	0.992	1	0.997	0.980	0.951	0.907	0.994

*Treatment effect is the reduction in cognitive progression as measured by the (1-CPR) relative to the blinded placebo arm.

Treatment Arm CPR*	H			
	Rand CPR 1.2	Rand CPR 1.1	Rand CPR 0.9	Rand CPR 0.8
0.80	0.171	0.407	0.893	0.981
0.75	0.412	0.685	0.970	0.996
0.70	0.688	0.868	0.989	1
0.65	0.879	0.953	0.994	1
0.60	0.962	0.984	0.998	1

*Treatment effect is the reduction in cognitive progression as measured by the (1-CPR) relative to the blinded placebo arm

Type I Error Rate

In this section, we focus on the null scenarios and type I error rates. The type I error rate of the design is a function of the model analysis, number of arms, sample size, and the design. In order to control the type I error rate, we simulate across a wide range of assumptions and null hypothesis for these parameters and demonstrate that the analysis controls the type I error rate at a one-sided 2.5% rate. The threshold for success at the final analysis is selected through simulation in order to control type I error rate. The primary DIAN-MCE analysis is based on the posterior probability of superiority ($CPR < 1$). That is, if in the final analysis the posterior probability of superiority is greater than the cut-off X , we will label the trial a success. The value of X is selected in order to control the type I error rate. In this section, we describe the procedure used to select X . In addition, we provide a post-trial permutation simulation procedure to verify the appropriateness of the type I error rate.

Simulate from the set of 13 null hypotheses. Each null scenario is simulated under the mathematical null hypotheses. The scenarios for E are mathematically identical to the base scenario when the active arm has no benefit. The scenarios for G are not considered mathematical nulls (when the rand effects are 0.70, 0.80, or 0.90) because the observational data are being used and the active drugs have an effect compared to the DIAN-OBS data. For each of the null scenarios, 1,000 simulated trials are presented. The posterior probability of superiority for each simulated trial is recorded. In each scenario, the 97.5th percentile is reported (this would be the value to control the type I error rate at 0.025 for that scenario). The 97.5th percentile is also reported for the combination of the 13,000 null simulated trials. The largest of these thresholds is selected as the value needed to control the type I error rate.

This 97.5th percentile for each of these 13 scenarios (and combinations) is presented in [Table 16](#). The simulated type I error rate, using a probability of superiority threshold of 0.981, is reported in the last column.

Table 16: The 97.5th Percentile of the Posterior Probability of Superiority for the Null Hypothesis Scenarios. Using these as the threshold in that scenario would create a type I error rate of 2.5%.

	Simulation Scenario	97.5 th Percentile	Type I Error [contact]
A	Base	0.9678	0.013
B	Larger EYO	0.9713	0.015
	Smaller EYO	0.9723	0.016
C	2.5% Annual Drop-Out	0.9628	0.016
	10% Annual Drop-Out	0.9664	0.015
D	Correlation 0.25	0.9683	0.016
	Correlation 0.50	0.9669	0.012
	Correlation 0	0.9589	0.010
	Increased SD	0.9734	0.017
	Decreased SD	0.9653	0.010
E	Slower Decline	0.9801	0.023
	Faster Decline	0.9632	0.011
F	OBS N = 120	0.9599	0.009
Combined Nulls		0.9684	0.014

Post-Trial Permutation of Type I Error Rate

To justify that the model behaves similarly for the simulated data and for the actual patient data and to further verify the type I error rate, we will perform a null hypothesis permutation with the complete trial data. The details of this planned post-trial simulation are presented below. This post-trial simulation will be included in the CSR as supportive analyses for type I error control and a pure frequentist analysis of the Bayesian analysis. We permute the treatment assignment for randomized patients 10,000 times and calculate the frequency of these permutations that achieve the success threshold for the posterior probability and the frequency of permuted trials that achieve

the observed posterior probability for each arm as a permutation p -value. The permuted treatment assignments are all considered “null” scenarios.

- Using all the randomized subjects, a random permutation of the treatment code will be conducted. This will permute the treatment code of the 140 randomized patients. The primary analysis (4-arm MDPM; including the DIAN-OBS data) will then be applied to each of the 10,000 permuted datasets to estimate the CPR and posterior probability of superiority.
- The frequency of 10,000 permuted trials in which the posterior probability of superiority is greater than the pre-determined threshold will be reported and labeled as the “post-trial simulated type I error” of the trial. No pre-trial thresholds will be adjusted.
- The frequency of the 10,000 permuted trials in which the posterior probability of superiority is greater than the actual posterior probability for each arm will be recorded and labeled as the permutation test p -values for each arm.

